## Activation of pDCs at the Tumor and Vaccine Site with a TLR Agonist

### Abstract

Although cancer vaccines offer significant promise, clinical effectiveness has yet to be realized. Effective vaccines may require inclusion of basic elements of the immune response which allow successful elimination of pathogens. It is now clear that strong adaptive immune responses are preceded by a potent innate immune response, triggered by pathogen-associated molecular patterns (PAMPs) that are recognized by immune cells expressing Toll-like receptors (TLRs). In the absence of TLR signaling, release of inflammatory cytokines by innate immune cells is sub-optimal, likely explaining why tumors are poor at eliciting antigen-specific adaptive immunity. Harnessing and adapting the mechanisms used by pathogens to induce effective specific immunity represents a very promising approach to improving antigen-specific antitumor immune responses. The plasmacytoid dendritic cell, the primary producer of type I interferons in the body, is a central mediator of inflammation in response to TLR activation and coordinates immune cell interactions which lead to a potent adaptive immune response. This inflammatory response is important not only to trigger strong T-cell priming, but also to induce inflammation at the target site which leads to enhanced T-cell migration and effector function. In our murine models, we have found that plasmacytoid dendritic (pDC) cells can lead to enhanced antigen-specific immune responses, partially through synergy with myeloid dendritic cells (mDC). In addition, we and others have found that pDC can be activated directly in vivo through specific toll-like receptor (TLR) ligands. In this proposal, we will test these concepts in melanoma patients and will utilize a vaccine in combination with a TLR agonist capable of activating both pDC and mDC in order to model the synergy observed in our murine system. We will measure T-cell priming in patients immunized in the presence or absence of TLR activation. Subsequent to T-cell priming, we will administer the TLR agonist at the tumor site in order to induce inflammation at sites of cutaneous metastases and will test the ability of this intervention to activate pDC at the tumor site and enhance T-cell migration into the tumor and T-cell effector function. Our goal is to identify principles which may be generalized towards improving cancer vaccines against other common cancers.

### 1.0 Objectives

#### 1.1 Primary Objective

To compare the ability of vaccines in combination with TLR stimulation at the site of vaccine (R848; Resiquimod) to vaccines alone in the ability to enhance the generation of circulating antigen-specific T-cells (T-cell priming).

#### 1.2 Secondary Objectives

- A. To evaluate the ability of **locally administered** TLR agonist (R848 gel) to activate innate immune cells at the gp100 (g209-2M) **vaccine site**.
- B. To evaluate the ability of R848 gel, administered at the **tumor site**, to:
  - i. Induce inflammation and upregulation of adhesion molecules on tumor vasculature
  - ii. Enhance T-cell infiltration into tumor
  - iii. Generate T-cells against additional tumor antigens, not present in the vaccine (i.e., antigen spreading).
  - iv. Mediate clinical response with measure of objective tumor response rate and progression free survival.

C. To assess the association between clinical response and laboratory parameters of T-cell priming, T-cell migration to tumor, and inflammation at the vaccine and tumor sites.

## 2.0 Background Drug Information

### 2.1 Natural antitumor immune responses are often weak compared with antiviral immune responses

The notion of whether the immune system is capable of recognizing, responding to, and eradicating established tumors was at one time a rather contentious and controversial issue . However, much evidence has accumulated over the past two decades, both in humans and in mouse models, and at the cellular and molecular level, to establish that immune cells can play an important role in inducing successful cancer regression . Multiple studies using different tumor models have shown that administration of immune cytokines, specific vaccines, and adoptive transfer of immune cells can all lead to effective tumor eradication in the appropriate setting . Nonetheless, it is true that all of these treatments rely on specific immune interventions for their success. The generation of effective natural immunity against established tumors is likely to be a very infrequent event, as evidenced by the clinical manifestation of tumors in non-immunocompromised hosts and by the fact that spontaneous regressions are very rarely observed.

By contrast, the natural generation of effective immunity against viral infections remains the rule rather than the exception. Multiple studies have demonstrated that viral infections frequently lead to the spontaneous generation of strong immune responses that are often not only capable of inducing viral clearance, but also in generating long-lived memory responses capable of protecting the host against re-infection . In the past ten years, a number of seminal research studies have shed much light on why viruses and other pathogens can elicit such potent and effective natural immune responses. We believe that harnessing and adapting the mechanisms used by pathogens to induce effective specific immunity represents a very promising approach to improving specific antitumor immune responses.

### 2.2 Activation of innate immunity is critical for the generation of effective adaptive immune responses

Effective antiviral immune responses are initiated through activation of innate immune cells, including NK cells, conventional myeloid dendritic cells (mDCs), and plasmacytoid dendritic cells (pDCs), by specific TLR ligands . Activation of innate immunity induces the production of proinflammatory cytokines which can directly activate cells important for the initiation of adaptive immune responses. Type I interferons (IFNs) and tumor necrosis factor (TNF- $\beta$ ), for example, are potent inducers of mDC maturation, inducing upregulation of major histocompatibility complex (MHC) and costimulatory molecules as well as production of IL-12, both of which are important for the priming of naïve T cells . In addition, the activation of NK cells by pDC, cytokines and TLR ligands may lead to increased lysis of virally-infected cells or tumors which, in turn, can provide antigen to mDCs for presentation to T cells. Activation of innate

immunity is important not only for the generation of antigen-specific T-cells, but also to induce inflammation at the pathogen site which leads to enhanced migration of antigen-specific T-cells to the infected tissue.

[figure not shown]
### 2.3 Plasmacytoid DCs represent a critical link between innate and adaptive immunity

As the major producer of type I IFNs (represented by IFN- $\alpha$  and IFN- $\beta$ ), pDCs represent one of the most important links between innate and adaptive immunity. Upon triggering of TLR7 or TLR9 by virus, pDCs rapidly produce large amounts of Type I IFNs, activate a variety of immune cells such as B cells, natural killer (NK) cells and macrophages, and differentiate into antigen presenting cells (APCs) to induce antigen-specific T cell responses. Both mDCs and NK cell activation can also be partially mediated by Type I interferons. IFN- $\alpha$ RC -/- mDCs are defective in the ability to adequately respond to viral infections, suggesting that interferon-producing pDCs may be critical for the activation of mDCs and subsequent development of adaptive immunity.

A number of lines of evidence suggest that pDCs may interact with mDCs to induce an enhanced adaptive immune response in the development of antiviral immunity. Activation of mDCs by double stranded RNA or viral infection has been shown to be dependent on exposure to IFN- $\alpha$ . In addition, HIV was found to be able to activate pDC, which could subsequently activate mDC upon co-culture. In addition, it has been recently demonstrated that pDCs may interact with lymph node mDCs in the generation of anti-HSV CTL.

### 2.4 Cancer vaccines have significant potential, but require considerable optimization

The identification of tumor antigens recognized by T-cells has allowed the development of rational cancer vaccine strategies. Current evidence suggests that cancer vaccines have the ability to increase the levels of circulating T-cells capable of recognizing tumor antigens. However, this has not led to significant tumor regressions in patients. For example, an analysis of the response rate in over 500 patients with metastatic melanoma treated with vaccines was under 3%. Our hypothesis is that this is due to inadequate activation of innate immunity at the site of immunization as well as at the tumor site itself. Lack of adequate

**Figure 1.** Immunization with a combination of CpG-activated pDC plus mDC significantly enhances antigen-specific CTL responses. Mice were immunized s.c. with purified pDC, mDC, or a combination of pDC and mDC (1:1) which were first co-cultured for 4 hours with CpG and OVA257-264 peptide (the total number of DCs injected were kept at the same level for all groups). Seven days after immunization, mice were bled and PBL were isolated. Ag-specific IFN- $\gamma$  production by immune cells was assessed by ELISPOT assay upon *in vitro* restimulation with or without OVA peptide. ELISPOT picture represents duplicate wells in each immunized group in the presence of OVA peptide stimulation.

inflammation at the vaccine site may lead to suboptimal T-cell priming, while equally

important; the lack of inflammation at the tumor site may lead to inefficient migration of T-cells back to the tumor.

## **2.5 *Plasmacytoid dendritic cells and myeloid dendritic cells synergize in their ability to generate antigen specific immune reactions, resulting in an enhanced antitumor response in vivo***

We hypothesized that by their capacity to activate innate immunity, pDCs would potentiate the function of mDCs when used in combination. Indeed, when purified murine pDCs and mDCs were co-cultured in the presence of antigen and a TLR activation stimulus, such as CpG, followed by in vivo administration, antigen-specific T-cell levels were higher than with the administration of either DC subset alone (figure 1). Since the total number of DCs was kept constant for all groups, the interaction between pDC and mDC in their ability to stimulate T-cells was synergistic and not simply additive.

Importantly, tumor reduction was also enhanced when mice were treated with the combination of activated, antigen-pulsed pDC and mDC compared to either DC subset alone (Figure 2). Treatment of tumors with a combination of pDC and mDC resulted in mice with both smaller tumors (Figure 2A) and enhanced survival (Figure 2B).

Since pDC and mDC synergize in the generation of antigen-specific T-cells, we propose to use a TLR agonist, R848, which is capable of activating both pDC and mDC through TLR 7 and 8, respectively, in combination with vaccine in order to induce antigen-specific T-cells in melanoma patients.

## **2.6 *TLR agonists can activate pDC and mDC and can induce inflammation***

### **a. R848 (Resiquimod)**

Resiquimod (also known as R-848) is a novel heterocyclic amine that acts as a dual TLR7 and TLR8 agonist and therefore is capable of activating both plasmacytoid dendritic cells (pDC), which express TLR7, and myeloid dendritic cells (mDC), which express TLR8. Resiquimod is a member of the imidazoquinoline family of IRMs, of which imiquimod has been most extensively characterized (and is in active clinical use for the treatment of actinic keratosis and basal cell cancer). Resiquimod is consistently more potent than imiquimod (50-100 fold) based on median minimum concentration required to elicit a 3-fold increase in IFN- $\alpha$ , TNF- $\alpha$ , and IL-12 production by human PBMC. Resiquimod can promote functional maturation of DC subsets as defined by enhanced expression of co-stimulatory molecules important for antigen presentation and T-cell activation.

Resiquimod is available in a gel formulation for topical use and has been used previously in clinical trials of herpetic lesions, actinic keratosis and anogenital warts. These studies revealed that topical resiquimod is well tolerated and capable of inducing inflammatory reactions consistent with activation of plasmacytoid and myeloid dendritic cells. As we have shown synergy between pDC and mDC in the induction of antigen-specific T-cell priming, we propose to utilize topical resiquimod over the vaccine site.

In a study of multiple doses of topical resiquimod applied to intact skin of the upper arm (1246-R848), with a maximum exposure of 2.5mg (1gm of 0.25% gel) 2x/week for 3 weeks, dose-related, but tolerable, systemic adverse effects consistent with systemic cytokine induction were observed. These included fever, chills, and transient neutropenia. Application site reactions including erythema, stinging, and pruritis were also observed. Dose-related increases in local cytokine production and T-cell infiltration were also reported.

[figure not shown]
Because the 0.25% dose provided the highest level of immune cell infiltration, we will plan to utilize a dose of 0.2% R848 2 times per week in our study (currently, this is the highest clinical grade formulation available), with the option of dose reducing to 1 time per week should patients not tolerate the treatment due to adverse reactions.

In murine models, we have found that TLR agonists, given at the site of vaccine, can enhance the generation of antigen-specific T-cells (T-cell priming).

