#### **3.4 R848 Resiquimod (gel)**

Resiquimod is solubilized in a single phase, translucent gel formulation composed of propylene glycol, colloidal silicon dioxide, and triacetin. The 0.2% Resiquimod gel is packaged in 3.5g multidose tubes. Topical resiquimod gel preparations are to be stored between 15C (59F) and 30C (86F) with excursions permitted to 4C (39F) and 40C (104F). R848, 0.2%, will be applied over the gp100(g209-2M) vaccine injection site each week.

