### **6.0 Treatment Plan**

All patients will receive the class I, HLA-A2 restricted gp100(g209-2M) peptide vaccine. Patients who are HLA-DP4 positive will also receive the class II restricted MAGE-3 peptide, in separate extremities. This will allow us to generate melanoma-specific CD8+ and CD4+ T-cells. The gp100(g209-2M) immune response will be our primary endpoint for assessment of T-cell priming, since we have extensive previous experience with this vaccine and believe that CD8+ responses are critical to the development of a strong antitumor immune response. The MAGE-3 peptide will be given in order to stimulate antigen-specific CD4+ T-cells, which we believe are also important in the generation of strong antitumor immunity. Patients positive for both HLA types will

receive both vaccines, gp100(g209-2M) and MAGE-3, for eight weeks. Patients who are HLA-A2 positive and HLA-DP4 negative will receive only the gp100 peptide for 8 weeks. There will be two arms in Part 1: Arm A is the peptide vaccines plus the TLR7/8 agonist, R848 and Arm B is the peptide vaccines only. All patients will be randomized to either Arm A or Arm B by CORe during the registration process. The randomization will be stratified by cohort (metastatic disease or adjuvant). In Arm A, R848 gel will be applied to the gp100(g209-2M) vaccine injection site immediately following the injection. The R848 gel will be allowed to air dry for 30 minutes and then covered with a gauze dressing. All vaccines will be administered subcutaneously and intradermally. The gp100(g209-2M) peptide will be administered in the same extremity weekly (every 7 days +/- 2 days) for 8 weeks. Similarly, in a separate extremity of eligible patients, the MAGE-3 peptide will be administered weekly (every 7 days +/- 2 days) for 8 weeks. Each syringe (a total of 4, 2 for gp100 and 2 for MAGE-3) will contain 1ml of peptide vaccine; 0.5ml of the vaccine in each syringe will be administered intradermally and the other 0.5ml will be administered subcutaneously at each injection site for a total of 4 sites.

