**All adverse events will be recorded according to this table:**

Attribution	Grade 1	Grade 2	Grade 3	Grade 4	Grade 5
Unrelated			X	X	X
Unlikely			X	X	X
Possible	X	X	X	X	X
Probable	X	X	X	X	X
Definitive	X	X	X	X	X

Exceptions to this rule will include events and laboratory abnormalities that represent common symptoms and abnormalities of melanoma and chemotherapy and/or have no clinical significance:

- Abnormalities in hematologic parameters due to myelosuppressive therapeutic effect:
  - i. Anemia, neutropenia, lymphopenia, thrombocytopenia
  - ii. Epistaxis or bleeding except for catastrophic CNS or pulmonary hemorrhage
- Common symptoms of cancer (unless grade  $\geq 3$ ) including:
  - i. Fatigue
  - ii. Weakness
  - iii. Bone, joint or muscle pain
  - iv. Alopecia
  - v. Loss of appetite, Nausea, Vomiting
  - vi. Chemistry abnormalities (phosphorus, calcium, glucose)
  - vii. Coagulation abnormalities (shortened PT, PTT, increased fibrinogen)
- Laboratory abnormalities:
  - i. LDH (increased or decreased)
  - ii. Alkaline phosphatase (increased or decreased)
  - iii. Low levels of the following: AST, ALT, creatinine, BUN, uric acid, bilirubin, albumin, total protein
  - iv. Electrolyte abnormalities (sodium, potassium, bicarbonate, CO2, magnesium)

Abnormal laboratory test results will be captured if intervention is required.

Based on the CTCAE v.4, any grade 3 or greater toxicity will result in a dose reduction of the application of R848 from twice a week to once a week, however we will still report this AE. In addition, if this is required in 3 patients, we will temporarily halt accrual so that we can reassess the study as indicated. Abnormal lab values that are considered clinically significant by the principal investigator will be tracked. The criteria used is based on our experience with this assay in patients, was that biologically significant response is considered to be  $\geq 0.1\%$  gp100(g209-2M) tetramer + cells in the CD8 + T-cell population, and an increase of  $\geq 2$  fold of gp100(g209-2M) tetramer + cells at any time point over the pre-vaccine levels. This is based on the sensitivity of detection using our current tetramers and immunologic reagents.

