## 11.0 Statistical Considerations

### Overview

This is a randomized phase II trial enrolling melanoma patients who are HLA-A2+ with or without HLA-DP4+. Patients of two separate types will be enrolled in separate cohorts. One cohort includes patients who are NED but at high risk for recurrence. The second cohort will include patients with non-visceral metastatic disease and must have at least two evaluable and biopsiable lesions to be eligible for the trial.

The trial will have two parts. In Part 1 (both cohorts), we will fairly randomize patients to receive either the gp100(g209-2M) +/-MAGE3 peptide vaccine plus a topical TLR 7 /8 agonist, R848, (Arm A) or the gp100(g209-2M) +/- MAGE3 vaccine alone Arm B). The randomization will be stratified by cohort. A total of 48 patients will be enrolled, 24 per arm. All patients will receive the gp100(g209-2M) vaccine (those who are HLA-DP4 + will also receive the MAGE3 vaccine) weekly (for 8 weeks) and the patients randomized to receive R848 gel will have the gel applied to the gp100(g209-2M) vaccine site weekly.

After 8 weeks of treatment on Part 1, Part 2 of the trial begins. In Part 2 (only patients in the metastatic disease cohort), the treating physician will divide the area of cutaneous lesions into regions, Region A and Region B and designate the two regions to receive or not to receive R848. At least one lesion will be randomly assigned to receive R848 from weeks 8 through 24, and one will not. One lesion from each region will be chosen for biopsy as outlined in section 7.3. If a patient has more than two evaluable lesions, we will stratify by lesion size to assure that the lesions will be comparable.

As a safety measure, if a patient's untreated lesions grow while treated lesions are stable or shrink, all lesions will be treated with R848. This will occur after the assessment of the primary endpoints of the study, so it will not affect the analysis of these endpoints.

In April 2015, the trial is being further modified to add an additional 20 patients with metastatic disease, all of whom will receive the the gp100(g209-2M) +/-MAGE3 peptide vaccine plus R848 (Arm C). These patients will not be part of the primary comparative study analysis of T-cell responses in the blood. The purpose of these patients is to provide additional information on characterizing tumor response, defined as at least a 50% shrinkage in tumor size by irRC criteria.

### Part 1

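### The mandatory grade 3 R848 reduction in section 8.0 has no stated scope and cannot be carried out on weekly Part 1 gel, and sections 6.0, 8.0 and 10.3 give different actions for overlapping toxicity

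*Combined protocol and SAP*

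**What the plan says.** **Frequency.** Section 2.6 (background) first discusses the vaccine site, "we propose to utilize topical resiquimod over the vaccine site", and later says "we will plan to utilize a dose of 0.2% R848 2 times per week in our study", "with the option of dose reducing to 1 time per week should patients not tolerate the treatment due to adverse reactions". The operative sections separate the two uses:

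- Part 1, vaccine site. Section 3.4: the gel "will be applied over the gp100(g209-2M) vaccine injection site each week". Section 6.0: "R848 gel will be applied to the gp100(g209-2M) vaccine injection site immediately following the injection", and "The gp100(g209-2M) peptide will be administered in the same extremity weekly (every 7 days +/- 2 days) for 8 weeks". Section 11.0, Overview: Arm A patients "will have the gel applied to the gp100(g209-2M) vaccine site weekly".
- Part 2, tumour lesions. Section 6.0: twice weekly, at intervals of three to four days.

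**Action on grade 3 or worse toxicity.** Section 6.0 (Part 2 text) gives an option to go from twice to once weekly. Section 8.0, below the adverse event table, makes it mandatory: a "dose reduction of the application of R848 from twice a week to once a week", with a temporary accrual halt if three patients need it. Section 10.3 gives such toxicity, when attributable to the peptides or R848, as an example under the removal criterion for adverse events. The opening paragraph of section 8.0 has a separate rule that stops entry once three patients have Grade III or worse toxicity.

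**Analysis.** Section 11.0, Part 1, compares the arms at week 8 with a Wilcoxon rank-sum test and gives the lowest rank to anyone who leaves the study before week 8.

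**The concern.** A safety rule has to be executable wherever it applies. The section 8.0 reduction is written for the whole study but describes a step that exists only under the Part 2 schedule. An investigator facing a grade 3 event at week 3 in Arm A finds a mandatory instruction that cannot be followed, an optional one written for another part of the trial, and a removal criterion that may or may not apply.

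Two things are at stake. The first is patient safety: the action is unclear, and so is whether the event counts toward the halt that is tied to reductions. The second is the primary comparison. Whether the patient stays or is removed decides whether an observed week 8 value or the lowest rank enters the test. In the randomised comparison only Arm A receives R848, so ambiguity about R848 toxicity falls on one arm.

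**Working it through.** The plan gives no figure for this point, so the check sets the texts side by side, counts applications and then illustrates the effect on the primary test.

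**1. Frequency by part and site**

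| Section | Site and part | Frequency |
|---|---|---|
| 2.6 | none named in the sentence | twice weekly |
| 3.4 | vaccine site | weekly |
| 6.0 | vaccine site, Part 1 | with each weekly injection, 8 weeks |
| 11.0 Overview | vaccine site, Part 1 | weekly |
| 6.0 | tumour lesions, Part 2 | twice weekly |

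The three operative statements for Part 1 agree. Only section 2.6 lacks a scope.

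**2. What the section 8.0 reduction does in each part**

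- Part 2, weeks 8 to 24 (16 weeks): full schedule 16 × 2 = 32 applications; once weekly throughout 16 × 1 = 16. The rule changes exposure.
- Part 1, 8 weeks: schedule 8 × 1 = 8. Once weekly is already the schedule, so the count stays at 8. The rule changes nothing.

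**3. Does a Part 1 grade 3 event count toward an accrual rule?**

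- Section 8.0, opening paragraph (three patients with Grade III or worse): yes. It is not limited by part or site.
- Section 8.0, below the table (three patients needing the reduction): unclear, because the reduction cannot be made.

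**4. Action for grade 3 or worse toxicity**

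| Section | Action | Scope |
|---|---|---|
| 6.0 | reduction optional | Part 2 text |
| 8.0, below the table | reduction mandatory | none stated; any such toxicity |
| 10.3 | example of a reason for removal | attributable to peptides or R848 |

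An attributable grade 3 event in Part 2 meets all three. In Part 1 it meets the last two, and the first of those cannot be carried out.

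**5. Illustration of what the unclear action can do to the primary test**

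Inputs from section 11.0: 24 per arm, effect 0.73 SD, one-sided test, final nominal level 0.0482.

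The plan's own figure is 80% power. A two-sample t-test gives 0.801 at 0.05 and 0.796 at 0.0482, so the figure reproduces.

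Effect of one lowest rank: each Arm A patient moved to the bottom loses on average 24 × Φ(0.73/√2) = 24 × 0.697 = 16.7 from the Mann–Whitney statistic. Its null SD is √(24 × 24 × 49/12) = 48.5. The test statistic therefore falls by about 16.7/48.5 = 0.34 SD per patient.

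Simulated Wilcoxon power (40,000 runs, normal data, level 0.0482, normal approximation with continuity correction):

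| Arm A patients given the lowest rank | Power |
|---|---|
| 0 | 77% |
| 1 | 65% |
| 2 | 50% |
| 3 | 33% |

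The number of removals is an assumption, since the documents give no expected rate. The simulation has no early exits in Arm B and ignores the interim look.

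**The case against.** The strongest reply is that twice weekly and weekly belong to different sites. The tumour-site sentence in section 6.0 uses the same rationale, frequency and step-down as the sentence in section 2.6, so section 2.6 most naturally previews Part 2. Likewise, the wording of the section 8.0 reduction fits Part 2, and nothing labels it a Part 1 rule. This largely stands: the Part 1 schedule is not in real doubt, and the defect in both places is missing scope.

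Two stronger readings are tempting and are not supported.

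- A reader might infer that Arm A exposure is uncertain by a factor of two, 8 against 16 applications over 8 weeks. That needs one background sentence to override three operative sections that agree. No treatment-plan text puts twice-weekly gel on the vaccine site.
- A reader might infer that no R848 toxicity rule operates in Part 1. The three-patient Grade III stop opening section 8.0 is not limited by part. The same paragraph takes patients with Grade III or worse autoimmune reactivity, local skin reactions excepted, off study. Section 10.3 also applies.

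What the reply does not remove is a mandatory rule without a stated scope that cannot be carried out in Part 1, alongside an optional and a removal instruction for overlapping events.

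**Conclusion.** The point holds as a conflict between stated rules. The operative schedules are weekly on the vaccine site and twice weekly on tumours; section 2.6 only needs its scope stated. The section 8.0 reduction cannot be executed on Part 1 gel. Part 1 events do not clearly count toward the halt tied to it, but they remain covered by the separate three-patient Grade III stop.

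The consequence for the primary analysis depends on how often the question arises. Under the assumptions above, each Arm A patient who is removed before week 8 rather than kept with an observed value costs roughly 12 to 17 points of power. With no such events the cost is nil. The wording itself does not alter the planned sample size or significance level.

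This should be corrected before further patients are treated. It does not invalidate the design.

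**What to change.** Amend sections 2.6, 3.4, 6.0, 8.0, 10.3 and 11.0 together so that each of the following is stated once for Part 1 vaccine-site gel and once for Part 2 tumour gel, and repeated consistently:

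1. the application frequency, with part and site named in section 2.6;
2. the action on grade 3 or worse toxicity, including whether it is optional or mandatory, whether it depends on attribution, and how it relates to removal under section 10.3;
3. which events count toward each of the two three-patient rules in section 8.0.

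In section 11.0, Part 1, say whether a patient whose gel or vaccine is stopped for toxicity before week 8 counts as having left the study and so takes the lowest rank.

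The clinical team decides which schedule and action apply; this review takes no position on that. The cost is a wording amendment with IRB approval. It needs no extra patients, visits or data.
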